#### **4.7.2 Study Treatment Discontinuation**

Patients must discontinue study treatment permanently if they experience any of the following:

- Pregnancy

- Evidence of more than 10 microbleeds and/or areas of leptomeningeal hemosiderosis (ARIA-H), including any present at baseline, as assessed by central review of MRI.
- Diagnosed with three recurrent, symptomatic ARIA-E events or exacerbations of previous events.

The primary reason for study treatment discontinuation should be documented on the appropriate eCRF. Patients who discontinue study treatment prematurely will not be replaced.

*Patients who discontinue from the study drug or who complete the study treatment and do not enter the OLE will be asked to return for the collection of safety and efficacy data 4, 16, and 52 weeks after administration of the last dose of study treatment.*

*Additionally all patients who discontinue from study drug early will be encouraged to return for subsequent visits, especially the Week 105 visit (early discontinuation of study treatment does not imply study discontinuation).*

#### **4.7.3 Study and Site Discontinuation**

The Sponsor has the right to terminate this study at any time. Reasons for terminating the study may include, but are not limited to, the following:

- The incidence or severity of adverse events in this or other studies indicates a potential health hazard to patients.
- Patient enrollment is unsatisfactory.
- Futility analyses from this or other studies with crenezumab suggest that treatment with crenezumab is likely not effective
- Sponsor determines it is in the best interest of the patients.

The Sponsor will notify the investigator if the study is placed on hold, or if the Sponsor decides to discontinue the study or development program.

The Sponsor has the right to close a site at any time. Reasons for closing a site may include, but are not limited to, the following:

- Excessively slow recruitment
- Poor protocol adherence
- Inaccurate or incomplete data recording
- Non-compliance with the International Conference on Harmonisation (ICH) guideline for Good Clinical Practice
- No study activity (i.e., all patients have completed the study and all obligations have been fulfilled)

## **5. ASSESSMENT OF SAFETY**

### **5.1 SAFETY PLAN**

Crenezumab is not approved, and clinical development is ongoing. The safety plan for patients in this study is based on clinical experience with crenezumab in completed and ongoing studies. The anticipated important safety risks for crenezumab are outlined below. Please refer to the crenezumab Investigator's Brochure for a complete summary of safety information.

Several measures will be taken to ensure the safety of patients participating in this study. Eligibility criteria have been designed to exclude patients at higher risk for toxicities. Patients will undergo safety monitoring during the study, including assessment of the nature, frequency, and severity of adverse events. In addition, guidelines for managing adverse events, including criteria for dosage modification and treatment interruption or discontinuation, are provided below.

Investigators will assess the occurrence of adverse events and serious adverse events at all patient evaluation timepoints during the study. All adverse events and serious adverse events, whether volunteered by the patient, discovered by study personnel during questioning, or detected through physical examination, laboratory test, or other means, will be recorded in the patient's medical record and on the appropriate adverse event eCRF. Each recorded adverse event or serious adverse event will include a description of its duration (i.e., start and end dates), severity, seriousness according to regulatory criteria, if applicable, and suspected relationship to the investigational product, as well as any actions taken. Patients will be carefully followed for adverse events during the study, including a safety follow-up period of 52 weeks after the last dose of study drug.

An iDMC will review unblinded safety and limited efficacy data at regular intervals (see Section 3.1.4 and the iDMC charter for further details).

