Neuroradiologic evaluation will use a standard MRI protocol (including T2\*-weighted gradient–recalled echo [GRE] and fluid–attenuated inversion recovery [FLAIR]). Screening MRIs will be read by a central reader who will exclude patients with other structural causes of dementia, significant cerebral vascular pathology, and other relevant exclusion criteria (see Section 4.2).

Patients will be eligible for the study whether or not they are receiving standard-of-care symptomatic medications for AD (i.e., ChEIs or memantine, or combination), or medical food *supplements* (e.g., Axona® or Souvenaid®). These medications or *supplements* must have been stable for  $\geq 3$  months prior to screening.

The study will consist of a screening period of up to 12 weeks for each patient who agrees to participate, signs the informed consent form, and is eligible for the study. Eligible patients will then undergo the baseline visit (Week 1), when they will receive the first dose following completion of all relevant assessments. Patients will be enrolled in a double–blind treatment period of 100 weeks (26 doses; 60 mg/kg *crenezumab* or *placebo* by IV infusion Q4W), and a final efficacy and safety assessment 4 weeks following the patient’s last dose (Week 105). Patients will then have the option to enter the OLE study if eligible. Patients who do not enter the OLE will have additional follow-up visits at 16 and 52 weeks after the last dose, primarily for safety and also for limited efficacy assessments. Assessments for patients who participate in the OLE will be documented in a specific OLE protocol.

*Patients who discontinue treatment before Week 105 should be encouraged to return for subsequent visits, for non-infusion related assessments, especially the Week 105 visit.*

[figure not shown]
Patients will undergo brain MRI examinations for monitoring of safety and as a biomarker to assess study drug activity. Patients will also undergo tests to monitor safety (including standard safety blood tests, ECG, MRI), as well as tests for cognition, function, and quality-of-life (QOL) assessments. Blood samples for assessment of pharmacokinetics, PD biomarkers, and for the measurement of antibodies directed

against crenezumab and other components of the drug product will be obtained from all patients.

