## **3.2 END OF STUDY**

The end of the study is defined as the date when the last patient, last visit (LPLV) occurs or the date at which the last data point required for safety analyses or safety follow-up is received for the last patient, whichever occurs later. LPLV for the double-blind treatment period is expected to occur 153 weeks after the last patient is enrolled (i.e., 52 weeks after the last dosing visit at Week 101) for those patients who do not enter the OLE.

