#### **3.3.2 Rationale for Long-Term Follow-Up**

The primary objective of the long term follow-up is to estimate the long-term safety of crenezumab. Assessments performed 16 and 52 weeks after the last dose of treatment will evaluate the effects of treatment on both efficacy and safety parameters over an extended period when no study drug is administered. These assessments will be conducted in all patients who discontinue treatment *early* or who complete the study but do not enter the OLE. These assessments will allow for the exploration of the long-term effects of exposure to study drug given that continued cognitive decline is expected in this patient population.

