#### **5.3.1 Adverse Event Reporting Period**

Investigators will seek information on adverse events at each patient contact. All adverse events, whether reported by the patient or noted by study personnel, will be recorded in the patient's medical record and on the Adverse Event eCRF.

**After informed consent** has been obtained **but prior to initiation of study drug**, only serious adverse events caused by a protocol-mandated intervention (e.g., invasive

procedures such as biopsies, discontinuation of medications) should be reported (see Section 5.4.2 for instructions for reporting serious adverse events).

*In addition, after initiation of a PET ligand but prior to initiation of study drug, all serious adverse events occurring within 48 hours of PET ligand administration should be reported regardless of relatedness to the PET ligand (see Section 5.4.2). After this 48-hour timepoint, only serious adverse events considered related to the PET ligand should be reported. Non-serious adverse events (occurring at any timepoint) considered to be related to the PET ligand should also be reported.*

**After initiation of study drug**, all adverse events will be reported until 2 elimination half-lives after the last dose of study drug (8 weeks) after the last dose of study drug.

Instructions for reporting adverse events that occur after the adverse event reporting period are provided in Section 5.6.

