### **5.4.2.2 Events That Occur after Study Drug Initiation**

After initiation of study drug, serious adverse events and adverse events of special interest will be reported until 8 weeks after the last dose of study drug. Investigators should record all case details that can be gathered immediately (i.e., within 24 hours after learning of the event) on the Adverse Event eCRF and submit the report via the electronic data capture (EDC) system. A report will be generated and sent to Roche Safety Risk Management by the EDC system.

In the event that the EDC system is unavailable, the Serious Adverse Event/Adverse Event of Special Interest Reporting Form provided to investigators should be completed and submitted to the Sponsor or its designee immediately (i.e., no more than 24 hours after learning of the event), either by faxing or by scanning and emailing the form using the fax number or email address provided to investigators. Once the EDC system is available, all information will need to be entered and submitted via the EDC system.

Instructions for reporting serious adverse events that occur >8 weeks after the last dose of study treatment are provided in Section 5.6.

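### The 52-week adverse event follow-up cannot be delivered while reporting closes at 8 weeks, and patients who stop drug early fall under two conflicting rules before Week 105

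*Combined protocol and SAP*

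**What the plan says.** Several passages describe long safety follow-up. Section 5.1 (Safety Plan) says "Patients will be carefully followed for adverse events during the study, including a safety follow-up period of 52 weeks after the last dose", and also "Investigators will assess the occurrence of adverse events and serious adverse events at all patient evaluation timepoints during the study". Section 3.1.1 gives patients who do not enter the OLE "additional follow-up visits at 16 and 52 weeks after the last dose, primarily for safety". Section 3.3.2 adds: "The primary objective of the long term follow-up is to estimate the long-term safety of crenezumab". Section 3.2 puts the last visit "52 weeks after the last dosing visit at Week 101", which is Week 153.

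The reporting rules are shorter. Section 5.3.1 opens with "Investigators will seek information on adverse events at each patient contact" but then closes reporting of all adverse events two elimination half-lives, given as 8 weeks, after the last dose. Section 5.4.2.2 applies the same limit to the more important events: "serious adverse events and adverse events of special interest will be reported until 8 weeks after the last dose of study drug". After that, Section 5.6 asks only for SAEs that come to the investigator's attention and are thought related to study drug. Section 5.3.5.8 sends later deaths to Section 5.6.

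In Appendix 1 Table 2 the adverse event row is marked from Week 57 to Week 105 and is blank at Weeks 117 and 153.

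Patients who stop drug early do not leave the study. Section 4.7.2 asks them back 4, 16 and 52 weeks after the last dose for safety and efficacy data, and encourages them to attend the remaining visits to Week 105. Section 6.4.1 repeats the request for safety data to Week 105. Section 5.1.2.1 keeps patients stopped for recurrent symptomatic ARIA-E in the study on the ordinary schedule.

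**The concern.** Two things go wrong. First, for completers who do not enter the OLE, the two visits meant mainly for safety come after reporting has closed and carry no adverse event assessment. The long-term safety estimate in Section 3.3.2 then has almost no event data behind it.

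Second, for patients off drug but still attending before Week 105, one rule says to record events at the visit and another says the reporting period is over. These visits lie inside the primary analysis period (Section 3.1.1), and Section 6.5 states no time window for counting events. Safety counts to Week 105 could therefore depend on which rule a site follows. If stopping differs by arm, the arms could be observed unequally.

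The events exposed are ones the protocol itself singles out. In the Phase II program there were 5 deaths on crenezumab and none on placebo (Section 1.2.3.2). Serious pneumonia occurred in 6 against 1, all 7 to 13 months after the first dose (Section 1.2.3.3). Section 1.3.6 relies on prompt reporting of pneumonia and deaths as a safeguard. Beyond 8 weeks off drug, such an event is required only if it is serious, is noticed, and is attributed to the drug.

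**Working it through.** **Calendar for completers.** Inputs: 26 doses every 4 weeks from Week 1 (Section 3.1.1), the 8-week close (Sections 5.3.1 and 5.4.2.2), and visits at +4, +16 and +52 weeks (Section 4.7.2).

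- Last dose: 1 + 4 × 25 = Week 101.
- Visits: 101 + 4 = 105, 101 + 16 = 117, 101 + 52 = 153. These match the Appendix 1 headers and the end-of-study statement in Section 3.2.
- Reporting closes: 101 + 8 = Week 109.
- Follow-up outside routine reporting: 153 − 109 = 44 weeks, and 44/52 = 84.6%.
- The Week 117 visit falls 117 − 109 = 8 weeks after closure. The Week 153 visit falls 44 weeks after it.

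**Are the blank cells real?** Table 2 has 15 visit columns (12 dosing visits, then Weeks 105, 117 and 153). The adverse event row has 13 marks. In the same table the CDR and ADAS-Cog-13 rows are marked at both late visits, so the blanks are not a loss in text extraction. Week 117 does have an ECG and PK, immunogenicity and plasma biomarker samples. Week 153 has only rating scales and questionnaires.

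**Patients who stop early.** Appendix 1 marks adverse events at each 4-weekly visit through Week 105. For a last dose at week L, reporting closes at L + 8. The first marked visit after closure is L + 12, and the count to Week 105 is (105 − (L + 12))/4 + 1. The values of L below are illustrative.

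| Last dose | Reporting closes | Weeks from closure to Week 105 | Marked visits after closure (maximum) |
|---|---|---|---|
| Week 25 | Week 33 | 72 | (105 − 37)/4 + 1 = 18 |
| Week 53 | Week 61 | 44 | (105 − 65)/4 + 1 = 11 |
| Week 77 | Week 85 | 20 | (105 − 89)/4 + 1 = 5 |

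The overlap arises for any last dose up to Week 93 (93 + 8 = 101, before Week 105). It disappears at Week 97 (97 + 8 = 105).

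The schedule also disagrees with itself here. For a last dose at Week 25, the +16 and +52 visits fall at Weeks 41 and 77. Both are marked for adverse events as study weeks but blank under the follow-up columns.

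**The case against.** The strongest reply is that the operative rules are consistent. Sections 5.3.1, 5.4.2.2, 5.6 and 5.3.5.8 all use the 8-week period, a half-life reason is given for it, and the schedule stops the adverse event row at Week 105. The concomitant medication and vital sign rows stop there too, so the blanks look deliberate. A reader might infer from the general statements about every timepoint and every contact that it is unsettled what sites record at Weeks 117 and 153. The documents do not support that: the specific limits and the schedule agree that nothing is routinely recorded. This part of the reply stands. It leaves the mismatch with Sections 5.1 and 3.3.2 in place, because a clear rule that collects nothing cannot serve the stated objective.

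It can also be said that following patients means following existing events to resolution (Section 5.5.1). But Section 5.1 speaks of assessing occurrence, and Section 5.5.1 sets no window for new events.

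On size, the visit counts assume full attendance, whereas Section 4.7.2 only encourages it, with emphasis on Week 105. No rate of stopping drug while staying in the study is given; the 35% in Section 6.1 is dropout. A reader might also take the 85% as a share of late events or of patients lost. It is a share of calendar time, and only for those outside the OLE, which Section 1.3.2 expects a large proportion to enter.

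Partial safeguards exist. Section 5.6 keeps related SAEs. Sections 4.7.1, 6.2 and 6.4.1 record and summarize withdrawal and its reasons, so an off-drug death could surface there, though not as an adverse event record.

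Finally, extending collection is a choice. Correcting the 52-week wording and adding a rule for early stoppers would also make the text consistent.

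**Conclusion.** The point holds in two parts. For completers not entering the OLE, the 52-week adverse event follow-up and its long-term safety objective cannot be delivered as written: 44 of 52 weeks and both late visits are outside routine reporting. For early stoppers who keep attending, there is a true conflict of rules inside the randomization-to-Week-105 period. It affects any last dose up to Week 93, with at most 18, 11 or 5 marked visits in the illustrative cases.

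Uneven recording between sites or arms before Week 105 is a risk, not an established fact, and the number of patients cannot be calculated from the documents. Two things were not available: the OLE protocol, and the separate SAP to which the protocol defers and which may define an adverse event window. The primary endpoint, power and alpha are unaffected. The text should be corrected, but this does not threaten the main efficacy conclusion.

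**What to change.** Reconcile Sections 3.1.1, 3.3.2, 5.1, 5.3.1, 5.3.5.8, 5.4.2.2, 5.6 and Appendix 1 as follows.

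- Keep 8 weeks after the last dose as the on-treatment analysis window.
- State that for patients off drug but still in the study, adverse events are recorded at the visits Appendix 1 already marks, through Week 105. This must include non-serious events, and ARIA reportable under Section 5.2.4. ARIA is a selected event and is not in the AESI list of Section 5.2.3, so a rule limited to SAEs and AESIs would miss non-serious cases.
- At the existing 16- and 52-week visits, record at least deaths, SAEs and AESIs (including pneumonia) regardless of causality. Show this as a footnoted adverse event mark at Weeks 117 and 153, so that the restricted scope is clear. If the sponsor does not want this, withdraw the 52-week adverse event statement and the long-term safety objective.
- Unless the separate SAP already provides it, add one by-arm summary of events through Week 105 in the Section 6.5 safety population (treatment actually received). Present later events descriptively, since patients who do not enter the OLE are a subset formed after randomization.

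The cost is a protocol amendment to the reporting text, two footnoted schedule cells and at most one extra summary. No new visits are needed. The downside is more off-drug events to process.

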#### **5.1.1 Amyloid-Related Imaging Abnormalities-Edema/Effusion and Amyloid-Related Imaging Abnormalities-Hemosiderin Deposition**

The occurrence of imaging abnormalities believed to represent amyloid-related imaging abnormalities-edema/effusion has been reported in association with the investigational use of compounds that are intended to treat Alzheimer's disease through the reduction of amyloid  $\beta$  in the brain. These imaging abnormalities have, in the majority of instances, been asymptomatic, and their presence has been detected by brain magnetic resonance imaging (Salloway et al. 2009; Sperling et al. 2011).

These magnetic resonance imaging signal hyperintensities seen in the parenchyma and leptomeninges are named **amyloid-related imaging abnormalities-edema/effusion** to cover the magnetic resonance imaging alterations seen in the fluid-attenuated inversion

recovery sequence thought to represent edema in the gray and white matter and effusion or extravasated fluid in the sulcal space (Sperling et al. 2011). Symptoms, when present in association with such imaging abnormalities, have been reported to include headache, worsening cognitive function, alteration of consciousness, seizures, unsteadiness, and vomiting.

**Cerebral microhemorrhages** in Alzheimer's disease have a point prevalence of 23% (Vernooij et al. 2008). One longitudinal study found that in patients with Alzheimer's disease the incidence of  $\geq 1$  microhemorrhage after a mean follow-up of 2 years was 12% (Goos et al. 2010). Recently, the occurrence of microhemorrhage has also been identified as an adverse event in anti-amyloid vaccination trials, and together with superficial siderosis, these events have been termed **amyloid-related imaging abnormalities-hemosiderin deposition** (Sperling et al. 2011). Limited data on amyloid-related imaging abnormalities-hemosiderin deposition occurrence are available, but a retrospective analysis in patients with Alzheimer's disease who were treated with anti-amyloid  $\beta$  antibodies with full effector function reported that 24 out of 207 patients (11.6%) developed amyloid-related imaging abnormalities-hemosiderin deposition (Sperling et al. 2012a). Acute occurrence of cerebral microhemorrhage is not always considered clinically significant (Greenberg et al. 2009). Study patients who received bapineuzamab and developed amyloid-related imaging abnormalities-hemosiderin deposition without amyloid-related imaging abnormalities-edema/effusion were clinically asymptomatic (Sperling et al. 2012a). However, the clinical significance of cerebral microhemorrhage is not yet fully understood.

Recent population-based studies have shown that cerebral microhemorrhages are common in community-dwelling elderly people, with high prevalence ranging from 10%–25% (Greenberg et al. 2009). Among those patients, approximately 70%–80% had 1 or 2 cerebral microhemorrhages (Cordonnier et al. 2011) and high numbers of cerebral microhemorrhages have been associated with future risk of ischemic and hemorrhagic strokes (Greenberg et al. 2009). In a longitudinal study in patients visiting a memory clinic, the incidence of new cerebral microhemorrhages (range, 1–19 per patient) within 2 years of that visit was approximately 12%, and the incidence was not related to diagnosis (type of dementia or disease severity) or *APOE $\epsilon$ 4* status (Goos et al. 2010). Taken together, accumulating evidence suggests that cerebral mHs are common in cross-sectional observational studies of healthy elderly subjects, and the increase in prevalence over time may be part of the natural history of aging, which indicates a specific underlying vascular pathologic state, in particular hypertensive vasculopathy or cerebral amyloid angiopathy.

When anti-amyloid  $\beta$  antibodies bind to amyloid deposited around blood vessels, an Fc $\gamma$ R-mediated immune response may be elicited. This compromises vascular integrity and results in amyloid-related imaging abnormalities-edema/effusion or amyloid-related imaging abnormalities-hemosiderin deposition. The hypothesis that Fc $\gamma$ R-mediated immune response may contribute to the occurrence of amyloid-related imaging

abnormalities-edema/effusion and/or amyloid-related imaging abnormalities-hemosiderin deposition is supported by results from clinical studies that have shown that patients with Alzheimer's disease who were treated with anti-amyloid  $\beta$  antibodies with full effector function developed amyloid-related imaging abnormalities-edema/effusion (symptomatic and asymptomatic). *In these patients ARIA events tend to occur early after treatment initiation and are dose and APOE  $\epsilon 4$  dependent.*

